Royal Derby Hospital, University of Nottingham Derby	[name] [contact]
[name]	Principal Research Fellow
Royal Derby Hospital, University of Nottingham Derby	[name] [contact]
[name]	Lecturer in Exercise Physiology and Metabolism
University of Birmingham Birmingham	[name] [contact]

Trial name:	The effects of prot	ein distribution and	d resistance exercise training o	on the muscle o	of older adults
Protocol version number:	6.0	version date:	10-Apr-17	Page:	3 of 31

TRIAL SUMMARY

Title

The effects of protein distribution and resistance exercise training on the muscle of older adults

Trial Design

Exploratory randomised trial and feasibility trial

Objectives

Principal objective: Investigate the effect of dietary protein distribution on muscle protein synthesis (MPS) over two weeks, with and without RET, in the thigh muscle of older adults Secondary objectives:

- (i) Investigate whether protein distribution influences serum inflammatory markers
- (ii) Consider the feasibility of manipulating daily protein distribution using diet plans, and investigating participant compliance to the diets
- (iii) Determine whether the effect of RET on muscle strength is influenced by protein distribution
- (iv) Investigate whether changes in responsiveness of MPS predict changes in muscle strength

Participant Population and Sample Size

We will recruit women aged 65 years or over and ambulatory (with or without walking aid) from the Birmingham 1000 Elders database, and through local community groups and leaflets in public areas As an exploratory and feasibility trial, a power calculation to determine sample size has not been completed due to lack of previous data. A sample size of n=10-12 has been decided upon for each group, giving a total sample size of n=20-24.

Outcome Measures

All outcome measures will be made by members of the study team (i.e., research nurses, the PhD student)

The primary outcome measure will be muscle protein synthesis

Secondary outcomes are:

- Serum inflammatory markers (IL-1, IL-6, IL-8, TNF-alpha, and the anti-inflammatory cytokine II -10)
- Leg extension strength in each leg
- Food diaries
- Outcomes relating to trial feasibility, including participants' willingness to be randomised, number of eligible participants, number of participants recruited, compliance with the study diets, adherence to exercise and the time taken to collect data

Muscle biopsies will be taken from the thigh at baseline and 2 weeks to measure muscle protein synthesis; at baseline a sample from one thigh will be taken, and at 2 weeks a sample from each leg will be taken, for comparison between exercised and non-exercised legs (see intervention). Saliva samples will also be taken at these times, and an additional saliva sample at 1 week, to allow calculation of MPS. 1-RM leg extension strength and serum inflammatory markers will be measured at baseline and after 2 weeks. 3-day food diaries will be completed at baseline and at the end of the intervention to determine compliance to the diet plan, and participants will be asked to complete a daily questionnaire to confirm whether they have eaten one of the study meals for each meal of the day (yes/no answers). All assessments will take place in the Wellcome Trust Clinical Research Facility.

Trial name:	The effects of prot	ein distribution and	d resistance exercise training o	on the muscle o	of older adults
Protocol version number:	6.0	version date:	10-Apr-17	Page:	4 of 31

Key Eligibility Criteria

Inclusion criteria are: Aged 65 years of over; female; ambulatory (with or without walking aids). Exclusion criteria are based upon previously published criteria for exercise studies and include:

- Already engaging in regular exercise (at least twice a week)
- History of myocardial infarction within previous 2 years
- Cardiac illness: moderate/ severe aortic stenosis, acute pericarditis, acute myocarditis, aneurysm, severe angina,
- Clinically significant valvular disease, uncontrolled dysrhythmia, claudication within the previous 10 years
- Thrombophlebitis or pulmonary embolus within the previous 2 years
- History of cerebrovascular disease (CVA or TIA) within the previous 2 years
- Treatment with anticoagulants (Warfarin, rivaroxaban, apixaban, dabigatran) and antiplatelets (dipyridamole, clopidogrel, prasugrel, ticagrelor, glycoprotein IIb/IIIa antagonists). Nb. those regularly taking aspirin will be asked to stop for 3 days prior to biopsies and restart the day after
- Acute febrile illness within the previous 3 months
- Severe airflow obstruction
- Uncontrolled metabolic disease (e.g., thyroid disease or cancer)
- Significant emotional distress, psychotic illness or depression within the previous 2 years
- Lower limb fracture sustained within the previous 2 years; upper limb fracture within the previous 6 months; non arthroscopic lower limb joint surgery within the previous 2 years
- Any reason for loss of mobility for greater than 1 week in the previous 2 months or greater than 2 weeks in the previous 6 months
- Resting systolic pressure >200 mmHg or resting diastolic pressure >100mmHg
- Poorly controlled atrial fibrillation
- Poor (chronic) pain control
- Moderate/ severe cognitive impairment (MMSE <23)
- Renal impairment (Stage 4 or 5)

Intervention

Participants will be randomised to RET (x3 per week) + Pulse protein distribution or RET + Spread distribution.

Protein distribution: Daily protein intake will either be consumed in a Pulse distribution (meals of 10%, 80% and 10% of daily intake) or a Spread distribution (3 x 33%). This will be achieved using a diet plan which, if followed, will give these distributions, and will provide 1.2 grams of protein per kilogram of body weight per day. There will be a level of flexibility in the diets to allow for dietary requirements and personal preferences, and preliminary data indicate that protein supplementation may be required for some individuals in order to reach a protein intake of 1.2 g.kg⁻¹.day⁻¹. A commercial protein supplement will be used for this.

Resistance exercise training: Throughout the trial participants will complete 3 RET sessions per week of a unilateral leg extension model (6 x 8 repetitions at 75% 1-repetition maximum). The use of a unilateral model will allow comparison between exercised non-exercised legs, as well as between treatment groups.

Trial name:	The effects of prot	ein distribution and	d resistance exercise training o	on the muscle o	of older adults
Protocol version number:	6.0	version date:	10-Apr-17	Page:	5 of 31

Trial Schema

Telephone screening: health questionnaire

Pre-trial visit: Consent, health questionnaire, vitals (height, weight, blood pressure, heart rate), MMSE, unilateral RET familiarisation, food diary instructions, activity monitor attachment

Day 0: Blood sample, saliva samples (x2), muscle biopsy, D₂O administration, diet plan administration, unilateral RET session

Weeks 1-2: Unilateral RET session (3 per week)
Day 7: D₂O dose and saliva samples (x2)
Week 2: food diary

Day 14: 1-RM measurement, blood and saliva samples, muscle biopsies (x2)

1.1. Background

Life expectancy in the UK is increasing, meaning the number of adults aged over 70 years is also growing, however this rate of increase is not matched by that of healthy life expectancy. Therefore, issues associated with healthy ageing are of great interest. One such issue which influences health in older age is sarcopenia, defined as the age-related loss of skeletal muscle mass and function. Sarcopenia is an important public health problem with a range of consequences. Loss of functionality makes it more difficult to carry out day-to-day activities and can result in loss of independence, which affects both quality of life and social care. Lower muscle mass is also associated with increased risk of falls¹, which can have serious health consequences for older adults, as well as disability, infection and mortality²⁻⁴. Hence, the design of effective interventions to combat sarcopenia has been a research goal for 30 years.

Although the causes of sarcopenia are multifactorial and not fully defined, one of the factors which is thought to contribute is the rate of muscle protein synthesis (MPS), and the responsiveness of MPS to anabolic stimuli. The basal rate of MPS in older adults is not different to that of younger adults⁵, but the rate in response to anabolic factors, such as protein or essential amino acid (EAA) ingestion or resistance exercise, is blunted compared to younger adults^{6,7}. This effect, known as anabolic resistance, translates into chronic maladaptation to anabolic factors8, and is thought to be one of the mechanisms behind sarcopenia. As a probable cause of sarcopenia, anabolic factors may also be a source of interventions to prevent sarcopenia; if the delivery of anabolic factors can be optimised to maximise MPS, this may translate into long term improvements in muscle mass and function. One component of delivery to consider is the distribution of protein intake. It has been suggested that ingesting protein in many small doses may repeatedly stimulate the MPS response, giving overall higher levels of synthesis. However, there is also the size of these doses to consider; division of the same amount of protein into a smaller number of larger doses may stimulate higher levels of MPS with each dose, giving overall higher output. This effect has been studied acutely in younger adults; participants fed three protein meals over 24 hours showed greater nitrogen retention than those fed smaller hourly meals^{9,10}, and in another study participants fed four protein doses of intermediate size had higher MPS than those fed either eight smaller or two larger meals¹¹. Studies testing this effect in older adults are relatively sparse. Arnal et al. 12 compared the effects of a Pulse diet, which provided 80% of daily protein at noon, with a Spread diet in which protein was spread more evenly over four meals, in 15 older women for two weeks, and found greater nitrogen balance, protein turnover and fat free mass (FFM) in the Pulse group. Bouillanne et al. 13 (2001) compared similar distributions in 66 older adults for six weeks, and reported greater improvements in indices of lean body mass (LBM), appendicular skeletal muscle mass (ASMM) and body cell mass (BCM) in the Pulse group. These two studies alone are not sufficient to develop recommendations regarding protein distribution, however they do indicate a possible role of protein distribution in preventing sarcopenia.

Resistance exercise training, another anabolic stimulus, has been more widely studied, and has consistently demonstrated improvements in muscle-related outcomes in older adults¹⁴. However, this response is still blunted compared to that of younger adults, and changes to the delivery of dietary protein, such as the distribution, may help to optimise the response and further improve the effects on muscle health. To date, no study in older adults has

Trial name:	The effects of protein distribution and resistance exercise training on the muscle of older adults					
Protocol version number:	6.0	version date:	10-Apr-17	Page:	10 of 31	

compared the protein distributions described above with a resistance exercise training programme. This study aims to fill this knowledge gap, which will contribute to the development of lifestyle interventions to act against sarcopenia.

Furthermore, as research in this area is so sparse, little is known as to the feasibility of this trial, particularly as previous studies of daily protein distribution in older adults have been of shorter durations (2-6 weeks). Hence, another aim of this study is to consider the feasibility of the trial in terms of diet compliance, as well as exercise adherence, participants' willingness to be randomised, number of eligible participants and number recruited, and the time taken to collect the data. This information could inform the design of future studies.

1.2. Trial Rationale

1.2.1. Justification for participant population

We have selected adults aged over 65 years as this aged group are most susceptible to the effects of sarcopenia, and so stand to benefit from interventions designed to improve muscle health. We have chosen to make this a single sex study, as older women display greater blunting of adaptation to RET than older men¹⁵, hence the inclusion of both men and women would affect the ability to interpret the results. Specifically, we have selected to only include women, as they experience greater loss of functional ability as a result of sarcopenia.

1.2.2. Justification for design

This standalone study is designed to measured acute effects of protein distribution in combination with resistance exercise. The study includes a unilateral RET component to allow measurement of effects with and without exercise. Protein distributions will be implemented through dietary manipulation to investigate whether this is feasible as a lifestyle intervention.

1.2.3.Choice of treatment

There is evidence to suggest that the distribution of protein intake may have an effect on muscle health in older adults, however this evidence is limited to two studies. Chronic resistance exercise training has been shown to be effective in improving muscle health, however no study has combined this with different protein distributions in older adults.

1.2.4. Sub-studies

None proposed

Trial name:	The effects of protein distribution and resistance exercise training on the muscle of older adults					
Protocol version number:	6.0	version date:	10-Apr-17	Page:	11 of 31	

2. Aims, Objectives and Outcome Measures

2.1. Aims and Objectives

We hypothesise that there will be a significant difference in muscle health with different protein distributions. Based on previous studies, we hypothesise that improvements will be seen in both groups, however there will be greater improvement in the Pulse group.

Principal objective: Investigate the effect of dietary protein distribution on muscle protein synthesis (MPS) over two weeks, with and without RET, in the thigh muscle of older adults Secondary objectives:

- (i) Investigate whether protein distribution influences serum inflammatory markers
- (ii) Consider the feasibility of such an intervention in this population
- (iii) Determine whether the effects of RET on muscle strength is influenced by protein distribution
- (iv) Investigate whether changes in responsiveness of MPS predict changes in muscle strength

2.2. Outcome Measures

All outcome measures will be made by members of the study team (i.e., research nurses, the PhD student).

The primary outcome measure will be muscle protein synthesis

Secondary outcomes are:

- Serum inflammatory markers (IL-1, IL-6, IL-8, TNF-alpha, and the anti-inflammatory cytokine IL-10)
- Leg extension strength in each leg
- Food diaries
- Feasibility of the trial, including participants' willingness to be randomised, number of eligible participants, number of participants recruited, compliance with the study diets, adherence to exercise and the time taken to collect data

Muscle biopsies will be taken from the thigh at baseline and 2 weeks to measure muscle protein synthesis; at baseline a sample from one thigh will be taken, and at 2 weeks a sample from each leg will be taken, for comparison between exercised and non-exercised legs (see intervention). Saliva samples will also be taken at these times, and an additional saliva sample after 1 week, to allow calculation of MPS. Serum inflammatory markers and 1-RM leg extension strength will be measured at baseline and 2 weeks, and the analysis metric will be change from baseline. Physical activity level will be measured before the start of the study to characterise the population. 3-day food diaries will be completed at baseline and in the final days of the intervention to determine compliance to the diet plan, and participants will be asked to complete a daily questionnaire to confirm whether they have eaten one of the study meals for each meal of the day (yes/no answers). All assessments will take place in the Wellcome Trust Clinical Research Facility.

Trial name:	The effects of protein distribution and resistance exercise training on the muscle of older adults					
Protocol version number:	6.0	version date:	10-Apr-17	Page:	12 of 31	

3. Trial Design and Setting

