6.2. Randomisation

Participants will be randomised in advance by [name] (UHB Statistician) using a computer generated programme, and concealed in sequentially numbered opaque envelopes. Blocked randomisation will be used for the first 20 participants to ensure at least n=10 in each group.

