13.2. Analysis of Outcome Measures

All data will be entered into a database. Using SPSS Statistics for Windows, Version 21.0. Armonk, NY: IBM Corp., data analysis will be conducted by the PhD student on both an intention to treat and per protocol basis (i.e. values for all measurements, completed at least 75% of exercise sessions, and complied with the study diet). Comparisons are planned between Pulse and Spread distribution groups for change in all outcome measures. In the case of MPS, a comparison between trained and untrained legs is also planned. All data will be checked for normality and appropriate log transformations applied prior to *t*-tests for primary and secondary outcome measures.

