13.2.5. Power Calculations

As an exploratory trial, the study has not been powered due to lack of previous data. Data from this trial will inform sample size calculations for future studies; the MRC Framework for Development and Evaluation of RCTs for Complex Interventions to Improve Health states that "the exploratory trial may be a vital source of estimates for the sample required for a main trial, an essential step since, as is frequently lamented, all too many trials prove to be under-powered". Specifically, a sample size of n=20-24 has been chosen due to practical considerations of time and cost.

14. Trial Organisational Structure

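### Strength and serum markers are compared by unadjusted t-tests on change: valid, but less precise than ANCOVA unless the baseline correlation is high, and with the log scale left open

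*Protocol*

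**What the plan says.** Section 2.2 lists five cytokines (IL-1, IL-6, IL-8, TNF-alpha and IL-10) and "Leg extension strength in each leg" as secondary outcomes. They are measured at baseline and at two weeks, "and the analysis metric will be change from baseline".

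Section 13.2 states the comparison: "Comparisons are planned between Pulse and Spread distribution groups for change in all outcome measures". It also states the preparation and the test: "All data will be checked for normality and appropriate log transformations applied prior to" t-tests, for primary and secondary outcomes alike. Neither section names a baseline covariate, and Section 13.2 does not say which quantity is to be logged.

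The Trial Summary gives the size: "A sample size of n=10-12 has been decided upon for each group, giving a total sample size of n=20-24". Section 13.2.5 says why no power is quoted: "As an exploratory trial, the study has not been powered due to lack of previous data". Section 6.2 balances numbers only: "Blocked randomisation will be used for the first 20 participants to ensure at least n=10 in each group". No stratification by a baseline value is described.

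**The concern.** A change score subtracts the whole baseline value from the follow-up value. When the correlation between the two visits is below 1, that is too much. An arm that starts high by chance tends to fall back, and the change score attributes this regression to the mean to the diet. With 10-12 per arm, sizeable chance imbalance is common. The surplus subtraction also adds noise, so the contrast has a larger variance than one adjusted for baseline by regression.

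The log step raises a separate question. Cytokine levels are often skewed, so a log scale is a natural choice, but the variable that enters the t-test is a change. If the log is taken of the change, it does not exist for a participant whose marker falls or stays the same. If it is taken of the levels before differencing, it works, but the result is then a ratio and no longer a difference. The protocol leaves this open and lets a normality check decide, which has little ability to detect skewness in 10-12 values per arm. The choice is made after the data are seen, by the person who runs the analysis, in a trial without blinding (Section 6.3).

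Secondary objectives (i) and (iii) rest on these contrasts.

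**Working it through.** The protocol states no SD, effect size, alpha or correlation, so there is no figure of its own to reproduce.

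**Inputs.** From the protocol: n = 10 to 12 per arm, N = 20 to 24; metric and test as above. Assumed: equal SD at both visits (the unit below), and a baseline-to-day-14 correlation r between 0.3 and 0.95.

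**1. How often imbalance occurs.** The SD of the difference in baseline means is √(2/n): 0.447 at n=10 and 0.408 at n=12. The chance of an imbalance above 0.5 SD in either direction is 2Φ(−0.5/0.447) = 2Φ(−1.118) = 26%, and 2Φ(−0.5/0.408) = 2Φ(−1.225) = 22%.

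**2. What it does to the change score.** Given a baseline imbalance b, the expected change-score contrast is the true effect + rb − b, so the error is −(1−r)b. With b = 0.5 and r = 0.6 this is −0.4 × 0.5 = −0.2 SD. For b = 1 SD it is −0.5 SD at r = 0.5 and −0.1 SD at r = 0.9. Averaged over repeated randomisation the error is zero.

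**3. Precision.** The variance of the change-score contrast is proportional to 2(1−r), and that of ANCOVA to 1−r². The ratio is (1−r²)/[2(1−r)] = (1+r)/2. Estimating the slope multiplies it by about 1 + 1/(N−4), which is 1.0625 at N=20 and 1.05 at N=24.

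| r (assumed) | (1+r)/2 | N=20 | N=24 |
|---|---|---|---|
| 0.3 | 0.65 | 0.69 | 0.68 |
| 0.5 | 0.75 | 0.80 | 0.79 |
| 0.7 | 0.85 | 0.90 | 0.89 |
| 0.8 | 0.90 | 0.96 | 0.95 |
| 0.9 | 0.95 | 1.01 | 1.00 |
| 0.95 | 0.975 | 1.04 | 1.02 |

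**4. Check by simulation** (8,000 runs per cell, two-sided 5%, n=10 per arm, with the true difference at each r set to give the change score nominal 80% power by the normal approximation). Power, change score against ANCOVA: 76% and 89% at r = 0.3; 75% and 84% at 0.5; 76% and 80% at 0.7; 76% and 75% at 0.9; 75% and 74% at 0.95. Type I error was about 5% for both methods throughout.

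**5. The order of log and difference.** Sections 2.2 and 13.2 allow two readings. In one, levels are logged and then differenced, which is computable whenever both levels are positive. In the other, the change itself is logged, which is undefined at or below zero. In simulated lognormal levels with no mean change, the log differences had excess kurtosis of about 0, against 3.9 to 72 for untransformed changes. The workable reading is therefore also the one that addresses skewness.

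**The case against.** The strongest reply is that nothing here is invalid. A t-test on change is a legitimate randomised comparison, unbiased over repeated randomisation and with its type I error intact. The outcomes are secondary, and the trial is exploratory and deliberately unpowered. All of this stands, and it limits the point to efficiency, conditional bias and an unsettled scale.

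Three stronger readings are tempting, and the documents do not support them.

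- A reader might infer that the log step cannot be carried out. Section 13.2 refers to the data and to suitable transformations; it never says that a change score is logged. Logging levels first fits the text. No count of participants lost to an undefined log can be charged to the plan.
- A reader might infer that baseline imbalance goes uncorrected. It is corrected with slope 1 and so over-corrected.
- A reader might infer that precision is always lost. At r of about 0.9 the two methods are level, and above that ANCOVA is slightly worse at this sample size. The protocol gives no r. A very high value should not be presumed for strength, because the schedule in Section 8.1 places the baseline 1-RM 14 to 28 days before day 0, hence 28 to 42 days before the day-14 test.

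It may also be said that such detail belongs in a statistical analysis plan, which is not shown. That is fair for the order of log and difference taken alone. It is not fair for the metric and the test, which the protocol fixes itself; a later plan using ANCOVA would depart from it.

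**Conclusion.** The point holds as an improvement to a valid analysis. For 1-RM strength and the five serum markers, ANCOVA on a baseline the trial already collects would have about 0.68 to 0.90 of the change-score variance if r lies between 0.3 and 0.7 at N=20 to 24. It would be about neutral at r = 0.9, and at most 4% worse at r = 0.95. It would also remove the over-correction of chance imbalance, 0.2 SD for a 0.5 SD imbalance at r = 0.6. These figures rest on equal SDs at the two visits, a linear relation, and an r that the documents do not give and that may differ between strength and cytokines.

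The scale is an ambiguity to settle. The protocol should state which quantity is logged, and the choice should not depend on a normality check in arms of 10-12.

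**What to change.** Amend Sections 2.2 and 13.2 as follows.

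- **1-RM strength:** ANCOVA of the day-14 value on arm and that leg's own baseline value, fitted separately for the trained and the untrained leg.
- **Serum markers:** log-transform the measured levels at both visits, for all participants and by prior decision. Fit ANCOVA of the log day-14 level on arm and log baseline, and report the baseline-adjusted ratio of geometric means with a 95% CI.
- **Change scores:** keep them as descriptive summaries.
- **If change scores are nevertheless retained for testing:** state that logs are taken of the levels before differencing, and for which markers.

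The cost is wording and one degree of freedom per model; no new data are needed. In variance, the worst case over the range considered is a loss of 1% at r = 0.9 and 4% at r = 0.95 with N=20 (nil and 2% with N=24), against a saving of about 31% at r = 0.3 and 20% at r = 0.5.
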